## **TIMELINE/ASSESSMENT PERIOD**

The schedule of events, appendix A, is described in the protocol v2.0, 08 September, 2020.

Data Base Lock is planned for September 2021

Analysis period will last September 2021 to October 2021.

CSR completion is planned for October to November period.

## **RANDOMIZATION**

Participants will be randomly assigned to one of two study groups. Randomization assignments will be determined prior to initiation of the study using a random size permuted block design. Randomization will be stratified by age group with participants divided into 2 age groups of 18-49 years and 50-65 years. After obtaining informed consent, the signed informed consent document will be faxed to the investigational pharmacy. Upon receipt, the investigational pharmacy will begin preparation of the study material infusion. Assignment will be communicated electronically using Medrio randomization system. Once the study drug material is prepared, it will be sent to the bedside for administration via the bedside nurse under the oversight of one of the site investigators and/or study coordinator. After

baseline hemodynamic assessments, participants will be randomized to either placebo or citrulline in a 1:1 fashion stratified by age group. The participants, nurses, physicians, study coordinators and investigators will remain blinded to whether participants are receiving placebo or L-citrulline throughout the study. The investigational pharmacy will be unblinded and will be responsible for maintaining the blinding of investigators, participants, nurses, and primary medical team. The investigational pharmacy will deliver the correct infusion(s) to the patient's bedside every 24 hours. The placebo and study drug solutions will be identical appearing on delivery to the ICU where the drug will be administered.

## **SAMPLE SIZE**

This study will accrue approximately 66 patients in a 1:1 fashion to account for 10% attrition. This sample size was determined on the basis of an expected time to intubation event in the placebo group derived from historical data on critically ill patients with COVID-19 infection (SARS-CoV-2) of 3 days (72 hours) +/- 3 days (72 hours). An acceptable effect size in the intravenous citrulline group would be delay in time to an intubation event of at least 6.5 days (156 hours). Thus, a two-sided log-rank test with an overall sample size of 60 patients achieves 81% power at a 0.05 significance level to detect a hazard ratio of 0.46 when the placebo group time to intubation is 3 days. The study is expected to last 12 months, of which patient accrual will occur in the first 6-9 months. The accrual pattern across time is uniform.

In terms of mortality, in patients who progress to acute hypoxic respiratory failure requiring ICU care, the mortality is 50%. With a sample size of 60 patients, the study will have 80% power to detect a difference between the group proportions of -33%. The mortality in the intravenous citrulline group is assumed to be 50% under the null hypothesis and 17% under the alternative hypothesis. Again, the mortality rate for the placebo group is assumed to be 50%. The test statistic used is the two-sided z-test with pooled variance with a 0.05 significance level.

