2.0 STUDY SUMMARY

Title: Prospective, Randomized, Double-Blind, Placebo-Controlled Phase II Trial of Intravenous L-Citrulline to Delay and Potentially Prevent the Need for Invasive Mechanical Ventilation for Acute Hypoxemic Respiratory Failure in Patients with COVID-19 (SARS-CoV2) Illness.

Objective: To evaluate safety and efficacy of a bolus loading dose and continuous intravenous infusion of L-Citrulline compared to placebo in patients hospitalized with COVID-19 infection (SARS-CoV-2).

Hypothesis: Intravenous L-citrulline administration will safely restore the homeostasis of nitric oxide synthase by increasing both plasma citrulline and arginine levels. We also reason that restoration of citrulline/arginine balance through citrulline administration will safely re-establish homeostasis of NOS, lower oxidative stress, and reduce inflammation, thereby delaying and potentially preventing the need for invasive mechanical ventilation in patients hospitalized with COVID-19 infection (SARS-CoV-2).

Study Design:	
Prospective, randomized, placebo-controlled, double-blind design.
 
 1. Enrollment: approximately 6-9 months 2. Plasma citrulline and arginine levels at day 4 will represent the primary biochemical variable. 3. Vasomotor stability, as measured using a vasopressor dependency index (VDI), through study day 10, will represent the primary safety variable. 4. The length of time from the initiation of the treatment to an intubation event for invasive mechanical ventilation measured in hours will represent the primary clinical outcome. 5. Patients will be followed until hospital discharge for mortality, ICU and hospital lengths of stay, and a requirement for invasive mechanical ventilation and non-invasive mechanical ventilation with high flow nasal cannula or BiPAP as additional clinical endpoints. A further comparison will be performed at D28 and D60 based on telephone follow up for those discharged earlier. 6. Patients will exit the study early (prior to 10 days) if they recover and no longer require oxygen therapy.

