6.2 Inclusion Criteria

Participant eligibility is determined based on the selection of criteria detailed below:

1. Age 18-65 years.
2. Clinical evidence of COVID-19 (SARS-CoV2) infection, defined as a positive COVID-19 laboratory test plus evidence of an acute hypoxic respiratory illness requiring oxygen.
3. Admitted and transferred to floor without intubation.

6.3 Exclusion Criteria:

Patients meeting any of the following criteria will not be eligible for participation in the study:

1. No consent/inability to obtain consent
2. Patient, surrogate, or physician not committed to full support
3. Malignant or other irreversible condition and estimated 28-day mortality $\geq 50\%$
4. Moribund patient not expected to survive 48 hours (as defined by primary medical team) from start of study infusion
5. End-stage Liver Disease as defined by Child-Pugh Score > 9
6. Currently enrolled in, or participated in another study of an investigational compound within the last 30 days
7. Pregnant female, or female who is breast feeding
8. Allergy to L-citrulline or arginine or any citrulline- or arginine-containing product
9. Patient not otherwise suitable for the study in the opinion of any of the investigators
10. Requirement for intubation and invasive mechanical ventilation before study enrollment

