## STUDY ENDPOINTS AND COVARIATES

**Table 1: Primary and Secondary Efficacy Endpoints**

Primary Clinical Efficacy Variables:	The primary clinical efficacy variable is time to intubation event in hours from the start of study infusion.
Secondary Clinical Efficacy Variables:	

1. All-cause hospital mortality

2. The requirement for intubation and invasive mechanical ventilation

3. Length of non-invasive mechanical ventilation in hours

4. Length of oxygen therapy in hours

5. Length of ICU stay in hours

6. Length of hospital stay in hours

7. Difference in proportion of patients intubated

8. Difference in proportion of patients intubated and on MV

Secondary Biochemical Efficacy Variables:	

1. Plasma levels of citrulline at 2 hours, 12 hours, and study days 2, 4, 8, 10.

2. Plasma levels of arginine at 2 hours, 12 hours, and study days 2, 4, 8, 10.

3. Plasma NOx levels at 2 hours, 12 hours, and study days 2, 4, 8, 10.

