### ***Length of Oxygen Therapy in Hours***

### ***Length of Non-invasive Mechanical Ventilation***

We will provide median and range of length of non-invasive mechanical ventilation separately for each treatment group. There is an expectation that some patients will not require mechanical ventilation; therefore, overall duration of mechanical ventilation will be modeled with a zero-inflated Poisson model using consent and post-infusion start time for two separate analysis.

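### The 81% power for time to intubation assumes nearly all 60 patients are intubated, which the plan neither states nor expects; the SAP's 80% mortality power is for a test it does not plan to use

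*SAP*

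**What the plan says.** **Primary endpoint.** SAP Sample Size and Protocol 10.4 carry the same statement: "a two-sided log-rank test with an overall sample size of 60 patients achieves 81% power at a 0.05 significance level", for an HR of 0.46 and a placebo time to intubation of 3 days. That time is "derived from historical data on critically ill patients with COVID-19 infection". On timing, "The study is expected to last 12 months, of which patient accrual will occur in the first 6-9 months". About 66 patients are accrued to allow for 10% attrition, and the intention-to-treat population is all randomised patients. The SAP's primary test is a log-rank test stratified by age group; Protocol 10.5 names a log-rank test without stratification.

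**Who may be intubated.**
- Protocol 6.2 admits patients who meet "Admitted and transferred to floor without intubation".
- Protocol 6.3, criterion 2, excludes "Patient, surrogate, or physician not committed to full support".
- The hypothesis in Protocol 2.0 is that citrulline acts on nitric oxide synthase and inflammation, "thereby delaying and potentially preventing the need for invasive mechanical ventilation in patients hospitalized with COVID-19 infection".
- The SAP, under Length of Non-invasive Mechanical Ventilation, says "There is an expectation that some patients will not require mechanical ventilation".
- Protocol 3.4 cites a series of 24 critically ill patients. Of these, 18 (75%) were invasively ventilated, or 18 of 21 (86%) once those with do-not-intubate directives are removed.

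**Mortality.** Both sample size sections give 80% power with 60 patients for 50% versus 17%, using a two-sided pooled z-test. The 50% is described as the mortality of patients who reach ICU care. SAP All-cause Hospital Mortality plans Fisher's exact test. Protocol 10.6.1 plans a chi-square test, with Fisher if needed. The SAP applies a Hochberg adjustment to secondary outcomes.

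**The concern.** A count of patients fixes the power of a log-rank test only once the share who have the event is known. Neither sample size section gives that share. If 81% corresponds to about 60 events in 60 patients, the calculation assumes near-universal intubation. That sits badly with a trial of non-intubated floor patients, in a plan that hopes to prevent ventilation and expects some patients not to need it.

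At stake is how a non-significant primary result is read. A reader would take 81% as the chance of detecting HR 0.46, when that chance depends on an assumption the documents do not disclose. The mortality figure has a simpler version of the same problem: the power quoted in the SAP belongs to a test that the SAP does not use.

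**Working it through.** **Inputs.** HR 0.46 (3/6.5 = 0.4615), two-sided alpha 0.05, 60 patients allocated 1:1, power 81% (SAP Sample Size, Protocol 10.4). Normal quantiles: 1.960 and 0.878, sum 2.838, squared 8.054.

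**1. Reproducing the 81%.** With 60 events:
- Freedman: Φ(√60 × 0.54/1.46 − 1.96) = Φ(0.905) = 81.7%.
- Schoenfeld: Φ(√60 × |ln 0.46|/2 − 1.96) = Φ(1.05) = 85.3%.

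The stated figure matches Freedman with every patient intubated.

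**2. Events needed for 81%.**
- Schoenfeld: 4 × 8.054/(ln 0.46)² = 32.22/0.603 = 53.4, so 54.
- Freedman: 8.054 × (1.46/0.54)² = 8.054 × 7.310 = 58.9, so 59.

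These are 90-98% of 60 patients (54/60, 59/60) or 82-89% of 66 (54/66, 59/66).

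**3. What the stated timing implies.** Twelve months less at most nine of accrual leaves about 90 days. With exponential times of 3 and 6.5 days, read as means or medians, more than 99.99% of each arm is intubated by day 90. The stated inputs therefore assume almost no patient escapes intubation.

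**4. Power when some patients are never intubated.** Simulation assumptions: constant hazards, HR 0.46, two age strata, no age effect. Model A: recovery censors patients at the same rate in both arms. Model B: all patients are at risk to one common horizon.

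Expected events with 60 patients and placebo probability 0.86:
- A: the citrulline probability is 0.46/(0.46 + 0.14/0.86) = 0.739; 30 × (0.86 + 0.739) = 48.
- B: the citrulline probability is 1 − 0.14^0.46 = 0.595; 30 × (0.86 + 0.595) = 44.

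Power of the SAP's stratified log-rank test (A/B):

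| Placebo intubation probability | 60 patients | 66 patients |
|---|---|---|
| All patients intubated, both arms | 81.0% | 84.3% |
| 86% | 72.0/72.4% | 76.2/76.0% |
| 75% | 63.9/64.5% | 68.8/68.5% |

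The unstratified test in Protocol 10.5 gives slightly more: at 86%, 73-74% with 60 patients and 76-78% with 66.

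An expected 54 events give about 77% under model A and 80-81% under model B. The Schoenfeld count therefore does not secure 81% under every censoring pattern. An expected 54 events would need a placebo probability of 93-98% with 60 patients, or 87-93% with 66.

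**5. Mortality, 50% versus 17%.** Normal approximation, 30 per arm, pooled proportion 0.335: Φ[(0.33√30 − 1.96 × √(2 × 0.335 × 0.665))/√(0.25 + 0.1411)] = Φ(0.80) = 78.8%, close to the stated 80%. Full binomial enumeration:

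| Test at two-sided 0.05 | 30 per arm | 33 per arm |
|---|---|---|
| Pooled z / chi-square | 79.0% | 84.0% |
| Fisher's exact | 70.8% | 75.9% |

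These are before Hochberg, which cannot raise them.

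**The case against.** **Some patients is not a number.** The SAP does not quantify how many will avoid ventilation, and 54-59 events would leave 7-12 of 66 patients never intubated. This stands in part: with all 66 analysed, the assumption is less extreme (82-89% intubated). But the power statement is made for 60 patients, where 81% leaves almost no room, and 66 patients do not restore 81% at a placebo probability of 86%.

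**The 86% is borrowed.** It comes from 18 of 21 critically ill patients (exact 95% interval 64-97%), while the trial enrols floor patients. This stands. The 86% is the cited rate that best fits the full-support exclusion, but it can only illustrate. The model matters too. If the same 86% of both arms would eventually be intubated and the drug only delays it, with HR 0.46 among those patients, power is about 28-31%.

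**The secondary endpoint.** The SAP lists "Difference in proportion of patients intubated" as a secondary variable. A reader might infer that the power assumption makes this difference close to zero and so contradicts the endpoint. The documents do not support that, because they set no time window for it. At day 10 the same exponential inputs give 96% versus 79% intubated (means) or 90% versus 66% (medians). A short window does not rescue the 81%, however: those day-10 fractions give about 47-52 events in 60 patients and formula powers of 71-80%.

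**Mortality is secondary,** and the SAP also plans log-rank and Cox analyses of time to death. That is true and limits the weight of this part. It does not make the quoted power apply to Fisher's test.

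**Conclusion.** The point holds. Both stated powers reproduce from their own inputs, so a reader who inferred an arithmetic error would be wrong. The fault is that the 81% rests on nearly all 60 analysed patients being intubated. That assumption is not stated, and it does not fit the plan's expectation that some patients will not be ventilated, its aim of prevention, or the 75-86% in its own cited series.

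Under constant hazards and HR 0.46, the shortfall at a placebo probability of 86% is about 9 points with 60 patients (81 to 72) and 5 with 66 (81 to 76), and larger at lower rates. A reader might infer that the trial's true power is 72%, or that more patients are needed. The documents support neither, because they give no intubation rate for the floor population.

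The mortality mismatch is confined to the SAP: about 71% for the planned Fisher test with the stated 60 patients, against 80% quoted. The 76% applies only if all 66 are analysed. Protocol 10.4 and 10.6.1 agree with each other. In both documents, a 50% rate described for patients reaching ICU care is applied to the whole placebo group.

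**What to change.** **Both sample size sections.** Replace the unqualified 81% with wording such as:

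> 81% power for HR 0.46 assumes about 60 intubation events, i.e. that nearly all of 60 patients are intubated; power is lower if some patients are never intubated. For illustration, with a placebo intubation probability of 86% (critically ill series, Protocol Section 3.4), constant hazards, HR 0.46 and the age-stratified log-rank test, power is about 72% with 60 patients and 76% with 66. No rate for the floor population is available.

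**SAP only.** Either restate mortality power for Fisher's exact test as about 71% (60 patients; 76% with 66), or adopt the chi-square test of Protocol 10.6.1 (79%; 84% with 66). Say that both are before Hochberg.

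**Both documents.** Note that the 50% mortality rate is stated for patients reaching ICU care.

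**Cost.** Wording in two sample size sections, plus the SAP mortality test if chi-square is chosen. The stated power becomes less favourable. Enrolment and the primary analysis are unchanged.

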10.4 Sample Size

This study will accrue approximately 66 patients in a 1:1 fashion to account for 10% attrition. This sample size was determined on the basis of an expected time to intubation event in the placebo group derived from historical data on critically ill patients with COVID-19 infection (SARS-CoV-2) of 3 days (72 hours) +/- 3 days (72 hours). An acceptable effect size in the intravenous citrulline group would be delay in time to an intubation event of at least 6.5 days (156 hours). Thus, a two-sided log-rank test with an overall sample size of 60 patients achieves 81% power at a 0.05 significance level to detect a hazard ratio of 0.46 when the placebo group time to intubation is 3 days. The study is expected to last 12 months, of which patient accrual will occur in the first 6-9 months. The accrual pattern across time is uniform.

In terms of mortality, in patients who progress to acute hypoxic respiratory failure requiring ICU care, the mortality is 50%. With a sample size of 60 patients, the study will have 80% power to detect a difference between the group proportions of -33%. The mortality in the intravenous citrulline group is assumed to be 50% under the null hypothesis and 17% under the alternative hypothesis. Again, the mortality rate for the placebo group is assumed to be 50%. The test statistic used is the two-sided z-test with pooled variance with a 0.05 significance level.

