## **ANALYSIS CONVENTIONS**

### **Statistical Significance**

Unless otherwise specified, statistical tests will be 2-sided for all analyses and the null hypothesis will be rejected at the significance level of  $\alpha = 0.05$ . P-values will be rounded to four decimal places before assessing statistical significance. In this Phase II study, no adjustment for multiple comparisons for the primary clinical, safety, and biochemical outcomes will be made. The multiplicity from testing secondary clinical, biochemical, and safety outcomes will be adjusted based on a Hochberg procedure (Sakamaki, 2013; Ye et al., 2012).

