## **SECONDARY ENDPOINTS**

### **Secondary Clinical Endpoints**

- All-cause hospital mortality
- The requirement for intubation and invasive mechanical ventilation
- Difference in proportion of patients intubated
- Difference in proportion of patients intubated an on MV
- Length of ICU stay in hours
- Length of hospital stay in hours
- Length of oxygen therapy in hours
- Length of non-invasive mechanical ventilation in hours

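### The 80% mortality power is stated at an unadjusted 0.05, but the SAP tests mortality under a Hochberg adjustment, where power is lower by an amount the plan does not fix

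*SAP*

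**What the plan says.** SAP, Sample Size, and protocol 10.4 carry the same mortality paragraph. Protocol 10.4 reads: "With a sample size of 60 patients, the study will have 80% power to detect a difference between the group proportions of -33"%. The rates are given in the SAP: "The mortality in the intravenous citrulline group is assumed to be 50% under the null hypothesis and 17% under the alternative hypothesis", and "Again, the mortality rate for the placebo group is assumed to be 50"%. The test and level follow: "The test statistic used is the two-sided z-test with pooled variance with a 0.05 significance level". On numbers and allocation: "This study will accrue approximately 66 patients in a 1:1 fashion to account for 10% attrition"; the power statement uses the 60.

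SAP Table 1 and the Secondary Clinical Endpoints list both place "All-cause hospital mortality" at the head of eight secondary clinical endpoints.

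SAP, Statistical Significance, sets a default that applies unless something else is specified: "statistical tests will be 2-sided for all analyses and the null hypothesis will be rejected at the significance level of" 0.05. It then leaves the primary outcomes unadjusted and says of the rest: "The multiplicity from testing secondary clinical, biochemical, and safety outcomes will be adjusted based on a Hochberg procedure". Mortality is not exempted, and neither document restates its power under the adjustment. The section also does not say whether the family is the eight clinical endpoints or all secondary outcomes together.

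For the analysis itself, the SAP section on all-cause hospital mortality plans Fisher's exact test for the proportion dead by discharge, with a log-rank test on time to death in addition. It does not say which of the two p-values enters the Hochberg procedure.

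**The concern.** A power figure describes one decision rule. The one printed here describes a z-test declared positive at p ≤ 0.05. The rule written in the SAP declares mortality positive at a Hochberg threshold. That threshold lies between 0.05/m and 0.05 for a family of m tests and depends on the other p-values.

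Mortality is the only secondary endpoint with a power claim, so the claim will shape how a non-significant mortality result is read. A reader who takes it as the outcome of an 80%-powered test would credit it with more evidence against the assumed 33-point reduction than the adjusted test can give.

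**Working it through.** **Inputs.** From SAP Sample Size: 30 per arm (60 patients, 1:1), placebo 50%, citrulline 17%, two-sided pooled z-test, 0.05. From SAP Statistical Significance: Hochberg for secondary outcomes. From SAP Secondary Clinical Endpoints: eight clinical endpoints.

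**1. Reproduce the stated figure.** Power = Φ[(d − z·SE₀)/SE₁], with
- d = 0.50 − 0.17 = 0.33
- pooled rate = (0.50 + 0.17)/2 = 0.335
- SE₀ = √(0.335 × 0.665 × 2/30) = 0.1219
- SE₁ = √[(0.50 × 0.50 + 0.17 × 0.83)/30] = 0.1142

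At 0.05, z = 1.960 and (0.33 − 1.960 × 0.1219)/0.1142 = 0.798, so power is 78.8%. Exact enumeration of all death-count tables gives 79.0%. The printed 80% is reproduced to about one point.

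**2. What Hochberg does to the level.** Order the m p-values. If the largest is at or below 0.05, all are rejected. If not, the next largest is compared with 0.05/2, and so on down to 0.05/m for the smallest. Mortality is therefore judged at the full 0.05 only when every other p-value in the family is also at or below 0.05, which makes 79% the ceiling. If no other endpoint is positive, the level is in practice 0.05/m.

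**3. Floor for eight clinical endpoints.** The level is 0.05/8 = 0.00625, z = 2.734, and (0.33 − 2.734 × 0.1219)/0.1142 = −0.028. Power is 48.9% by formula and 51.3% by enumeration.

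**4. Full step-up procedure.** Simulation used 200,000 replicates per scenario, binomial deaths at the stated rates, and the other endpoints as independent normal statistics, either null or each with 80% power.

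| Family | Other endpoints | Pooled z-test | Fisher's exact |
|---|---|---|---|
| None (unadjusted 0.05, exact) | – | 79% | 71% |
| 8 clinical | no effect | 51% | 41% |
| 8 clinical | each 80% power | 66% | 55% |
| 13 pooled (assumed) | no effect | 44% | 35% |
| 13 pooled (assumed) | each 80% power | 57% | 47% |

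The family of 13 is an assumption: the eight clinical endpoints, three biochemical variables in SAP Table 1 and two safety variables in SAP Table 2.

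**5. Does enrolling all 66 restore the claim?** No. With 33 per arm the z-test at 0.05/8 has 54.5% power by formula.

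**6. Separating two effects.** The drop within the z-test column is due to multiplicity alone. The Fisher column adds the loss from the planned test being more conservative than the one used for sizing.

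**The case against.** The strongest reply is that the printed number is correct for what it declares. It states its test, rates, N and level, and on those terms 80% is right to about a point. Quoting per-comparison power for a secondary endpoint is common, and the trial is sized on time to intubation, not on mortality. That stands: this is not a miscalculation, and it does not bear on the primary sample size. But the sentence says without qualification what power the study will have, while the same document sets a different criterion for declaring a mortality effect.

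A second reply is that 0.05/8 is the worst case for that family. It supposes a drug that cuts deaths from 50% to 17% and leaves intubation and length of stay untouched, although the trial is premised on a hazard ratio of 0.46 for intubation. That also stands, and it is why the floor should not be quoted alone.

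A third is that eight overstates the number of distinct tests. The SAP gives three intubation endpoints the same analysis, and the heading for length of oxygen therapy has no method under it. Counting five distinct clinical tests, the z-test simulation gives about 59% with the others null, 72% with each at 80% power and 75% with each at 90%. The shortfall can therefore be small.

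A reader might infer from the eight-endpoint calculation that true mortality power is a fixed range of roughly 50% to 65%. The documents do not support that. The SAP does not define the family, Hochberg has no single level, and the z-test ceiling remains 79%.

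**Conclusion.** The point holds as a mismatch between a power statement and the decision rule it is meant to describe. The unqualified 80% is a nominal, unadjusted figure. Under the written Hochberg rule it can be approached only if all other secondary outcomes in the family also reach 0.05.

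For the z-test used in sizing, the loss from 79% is about 13 to 28 points with the eight clinical endpoints as the family (66% to 51%) and about 22 to 35 points with an assumed pooled family of 13 (57% to 44%). For the planned Fisher test, power starts at 71% and falls to between 55% and 41% in the eight-endpoint family. The results rest on the plan's rates and 30 per arm. The step-up figures also rest on an assumed family, independent endpoints, and assumed effects on the others.

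The consequence is limited to how a mortality result is interpreted. A reader might conclude that the trial is undersized or that the Hochberg rule is wrong. Neither follows, because mortality does not drive N and adjusting secondary outcomes is a reasonable choice.

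**What to change.** In SAP Sample Size and protocol 10.4:

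- Remove the unqualified 80% claim. Label the figure as nominal and unadjusted: about 79% for the pooled z-test, or 71% for the Fisher's exact test that the SAP plans.
- State in SAP Statistical Significance which endpoints form the Hochberg family, and which mortality p-value (Fisher or log-rank) enters it.
- Add the power under Hochberg for the planned test and that family. For example: about 41% at 0.05/8 if mortality is the only positive result among the eight clinical secondary endpoints, and higher if others are also positive (about 55% if each of the other seven has 80% power).

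This costs wording only. N, the data collected and the Hochberg rule stay as they are. The one drawback is that the stated mortality power becomes less favourable.
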